3. INTRODUCTION

As per ICH E9 (1) the purpose of this document is to provide a more technical and detailed elaboration of the principal features of the analysis described in the protocol, and to include detailed procedures for executing the statistical analysis of the primary and secondary variables and other data.

This TSAP assumes familiarity with the Clinical Trial Protocol (CTP), including Protocol Amendments. In particular, the TSAP is based on the planned analysis specification as written in CTP Section 7 “Statistical Methods and Determination of Sample Size”. Therefore, TSAP readers may consult the CTP for more background information on the study, e.g., on study objectives, study design and population, treatments, definition of measurements and variables, planning of sample size, randomisation.

INBUILD®-ON is the open-label extension of INBUILD® trial 1199.0247 which is also called parent trial throughout this document. Therefore, this TSAP also assumes familiarity with the TSAP of INBUILD® trial 1199.0247.

Unless stated otherwise SAS® Version 9.4 or later will be used for all analyses.

4. CHANGES IN THE PLANNED ANALYSIS OF THE STUDY

Kaplan-Meier analyses and descriptive statistics were added for the following:

- Time to first liver enzyme elevation (see [Section 5.4.4.1](#) for details)
- Time to first dose reduction (see [Section 5.4.3.1.1](#) for details)
- Time to first treatment interruption (see [Section 5.4.3.1.1](#) for details)
- Time to premature treatment discontinuation (see [Section 5.4.3.1.1](#) for details)
- Time to first dose reduction or treatment interruption (see [Section 5.4.3.1.1](#) for details)

All times mentioned above are considering the extension trial only.

There are several terms than can be used interchangeably for the Investigational Medicinal Product (IMP) in this trial such as “trial drug”, “trial medication”, “study drug”, “study medication”, or even “nintedanib” as this is an open-label trial.

5. ENDPOINTS

For endpoints or other variables where derived “last contact date” is utilised, e.g. time-to-event analyses, the following will apply:

The derived last contact date when the subject was known to be alive is defined as the latest date recorded in the electronic Case Report Form (eCRF) from the dates listed below (in case a date is planned to be imputed for the analysis, the imputed date will also be used):

- Last visit date,
- Last reported Adverse Event (AE) date (excluding end dates when outcome is fatal or unknown),
- Last reported concomitant therapy date,
- Last laboratory sample date,
- Last reported nintedanib intake date (non-imputed),
- Last reported dose change / interruption date,
- [REDACTED]
- Last contact date as collected on the end of study eCRF page (if reason for non-completion is not “Death”).

5.1 PRIMARY ENDPOINT

The primary endpoint is the incidence of overall adverse events over the course of this extension trial.

5.2 SECONDARY ENDPOINTS

Not applicable.

5.2.1 Key secondary endpoints

Not applicable.

5.2.2 Secondary endpoints

Not applicable.

5.4 OTHER VARIABLES

5.4.1 Demographics and baseline characteristics

5.4.1.1 Demographic data

- Gender (Male; Female)
- Ethnicity (Hispanic/Latino; Not Hispanic/Latino)
Note: For this study collection of ethnicity was not allowed at sites in France as per French law.
- Race: single race respondents, multiple race respondents (all combinations ticked), and all race categories regardless of how many race categories were ticked
Note: For this study collection of race was not allowed at sites in France as per French law.
- Age [years] at time of informed consent (IC) in extension trial (transferred by IRT) as continuous variable and in categories:
<30 years; >=30 to <45 years; >=45 to <60 years; >=60 to <75 years; >=75 years

- Age [years] at time of IC in parent trial (transferred by IRT) as continuous variable and in categories:
<30 years; >=30 to <45 years; >=45 to <60 years; >=60 to <75 years; >=75 years
- Weight [kg] (at inclusion in extension trial, i.e. Visit 1) as continuous variable and in categories: <30 kg; >=30 to <60 kg; >=60 to <90 kg; >=90 kg
- Height [cm] (at inclusion in extension trial, i.e. Visit 1) as continuous variable
- Body mass index [kg/m²] (at inclusion in extension trial, i.e. Visit 1), calculated as

$$\frac{\text{Weight [kg]}}{\text{Height [m]} * \text{Height [m]}}$$

as a continuous variable and in categories:

< 18.5 kg/m²; >=18.5 to <25 kg/m²; >=25 to <30 kg/m²; >=30 kg/m²

- Smoking status (Never; Current; Former)
- Pack years (for subjects with smoking status “*Current*” or “*Former*”) as continuous variable and in categories: <20 pack years; >=20 to <40 pack years; >= 40 pack years
- Duration of exposure to trial drug in parent trial will be calculated based on first and last trial drug intake in parent trial in days as

Date of last trial drug intake - Date of first trial drug intake + 0.5 days,

assuming that only one capsule was taken on day of last trial drug intake. In case of first trial drug intake was at 2:30 p.m. or later another half day will be subtracted. Duration in months will then be calculated as

$$\frac{\text{Duration of exposure to trial drug in parent trial [days]}}{30.5}$$

Duration of exposure to trial drug in parent trial will be summarised as continuous variable [months] and in categories:

- <=12 months (365 days);
- >12 to <=18 months (547 days);
- >18 to <=24 months (730 days);
- >24 to <=30 months (912 days);
- >30 months

5.4.1.3 Baseline characteristics for lung function

- FVC [mL] (at inclusion in extension trial, i.e. Visit 1)
- FVC [% pred] (at inclusion in extension trial, i.e. Visit 1)
- FEV1/FVC (at inclusion in extension trial, i.e. Visit 1)

5.4.2 Compliance

Only compliance in the extension trial will be considered.

5.4.2.1 Over the whole trial

Compliance [%] will be calculated as:

$$\frac{\text{Number of capsules actually taken}}{\text{Number of capsules which should have been taken}} \times 100\%$$

The number of capsules which should have been taken over the whole trial will be calculated as:

$$(\text{Duration of exposure over the whole trial}) \times 2,$$

using duration of exposure as defined in [Section 5.4.3.1](#) below. In case of dose reduction to 100 mg bid, the number of capsules taken per day is still 2, so the calculation of compliance remains the same. Only treatment interruptions not due to AE will be considered as a compliance issue, i.e. duration of interruptions due to AE will be subtracted from the duration of the treatment period for compliance calculation.

Compliance [%] will be summarised as continuous variable and in categories: <50%; >=50 to <80%; >=80 to <=120%; >120%.

If the amount of capsules taken is not reported for at least one expected visit or no final compliance assessment on or after the day of last trial drug intake is available the compliance will not be calculated.

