Diagnosis	Progressive Fibrosing Interstitial Lung Disease
Main in- and exclusion criteria	Patients who have completed the 1199.247 (INBUILD®) study and did not prematurely discontinue trial medication
Test product(s)	Nintedanib
dose	Nintedanib 150 mg bid (300mg daily) or 100 mg bid (200mg daily)
method and route of administration	p.o.
Comparator product(s)	Not applicable

Proprietary confidential information © 2020 Boehringer Ingelheim International GmbH or one or more of its affiliated companies

dose	
method and route of administration	
Duration of treatment	Treatment duration of at least 96 weeks or until nintedanib can be made available to the patient outside of the clinical trial. Treatment will be stopped if a reason for withdrawal is met.
Statistical methods	Descriptive statistics of adverse events and other safety parameters, [REDACTED]

FLOWCHART

Visit*	1 ²	2	3	4	5	5a	6	6a	7	7a	8	X ⁷	EOT ⁸	FU ⁹
Open Label Treatment Period														
Week	0	2	4	8	12	18	24	30	36	42	48	60+ every 12w		FU
Day	1	15	29	57	85	127	169	211	253	295	337			+28
Time window (days)		±3	±3	±3	±3	±7	±7	±7	±7	±7	±7	±7	±7	+7
Informed consent ¹	X													
Demographics ³	X													
Medical History ³	X													
Baseline Conditions	X ⁴													
Physical examination, vital signs	X	X	X	X	X		X		X	X	X			
Adverse events, conc. Therapy	X ⁴	X	X	X	X		X		X	X	X	X ¹⁰		X ¹⁰
12-lead ECG	X						X				X			
Safety laboratory	X	X	X	X	X	X ⁵	X	X ⁵	X	X ⁵	X	X	X	
Pregnancy test ⁶	X	X	X	X	X	X	X	X	X	X	X	X	X	
	X		X		X		X		X		X	X	X	
			X		X		X		X		X	X	X	
In/Exclusion criteria	X													
IRT call/notification	X		X		X		X		X		X	X	X	
Dispense trial medication	X		X		X		X		X		X	X	X	
Collect trial medication			X		X		X		X		X	X	X	
Compliance / drug accountability			X		X		X		X		X	X	X	
Termination of trial medication													X	
Conclusion of patient participation												X	X	

Footnotes:

* In case of dose change (reduction or re-escalation) additional visits may have to be scheduled (refer to section [6.2.2](#))

¹ The patient is required to sign informed consent prior to any trial related activities.

² Visit 1 will occur on the same day as EOT_B in INBUILD®. Laboratory tests, physical examination, vital signs, pregnancy test, ECG and spirometry tests are performed only once on that day as part of the EOT_B visit in INBUILD®.

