If blood sampling for central lab at the trial site is not possible, safety lab analyses can be performed at a local lab. The results of the lab tests must be transferred to the investigator who ensures medical review and proper documentation in the eCRF. Minimum required safety lab parameters are AST, ALT, GGT, ALK and Total bilirubin. For patients who have been in the trial for at least 36 weeks, the maximum interval between two lab measurements for these parameters is 16 weeks. If the interval is more than 16 weeks, trial treatment should be interrupted (refer to section [4.2.1](#)). These measures relating to lab sampling were not possible early in the trial when frequent monitoring was mandatory.

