Dispensation of study treatment on site	
• Site / depot to patient IMP shipments• Patients must consent to providing contact details for shipping purposes• Patients should retain all unused IMP and packaging, and return it when they are able to return to the site.

[figure not shown]

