5.4.2.2 Over 48 weeks and over 96 weeks

The number of capsules which should have been taken over 48 weeks and over 96 weeks respectively will be calculated as:

$$(Date \text{ of } last \text{ nintedanib } intake^{[1]} - Date \text{ of } first \text{ nintedanib } intake + 1) \times 2$$

^[1] Or Week 48/Week 96 compliance assessment, if earlier.

In case of last nintedanib intake happened until Week 48/Week 96 compliance assessment, half a day will be subtracted assuming that only one capsule was taken on day of last nintedanib intake.

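### One unreported capsule count deletes a patient's whole-trial compliance, and the 48/96-week denominator omits the AE-interruption subtraction used for the whole trial

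*SAP*

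**What the plan says.** **Whole trial (SAP 5.4.2.1).** Compliance is capsules taken divided by capsules expected, where expected is exposure duration times two. A separate sentence says that only interruptions not caused by an AE count against the patient: "duration of interruptions due to AE will be subtracted from the duration of the treatment period for compliance calculation". The last paragraph of the section sets the missing-data rule. The value is not calculated "If the amount of capsules taken is not reported for at least one expected visit", and also not if there is no closing assessment on or after the day of last intake. No partial-data alternative is given.

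**48 and 96 weeks (SAP 5.4.2.2).** The section opens "The number of capsules which should have been taken over 48 weeks and over 96 weeks respectively will be calculated as" and gives (last intake, or the Week 48/96 compliance assessment if earlier, minus first intake, plus 1) times 2, with a half-day correction. It has no AE-interruption term, no missing-count rule and no reference back to 5.4.2.1. The parallel exposure section, SAP 5.4.3.2, does refer back to 5.4.3.1 for its remaining variables.

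**Remote conduct (Protocol 10.3).** The minimum content of a home or remote visit is AEs, concomitant treatment and drug interruption; a capsule count is not in that list. On leftover drug: "Patients should retain all unused IMP and packaging, and return it when they are able to return to the site".

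**Deviation C3 (SAP Table 6.2: 1).** This is compliance above 120%. If overall compliance is missing, a negative eCRF answer on taking medication as instructed, at a visit where compliance cannot be calculated, flags the deviation. The flag is subject to manual review, and no patient is excluded.

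**The concern.** In an uncontrolled long-term safety trial, compliance helps the reader judge how far the AE profile reflects drug actually taken. Two features weaken the planned summary.

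First, the missing-count rule works against long follow-up. Each further visit is another chance to lose the whole value, so patients with the longest exposure are the most likely to drop out of the table. Remote visits and deferred returns make gaps foreseeable: version 1 of the SAP (December 2020) came after the protocol amendment of September 2020, yet the SAP says nothing about bridging a missed count.

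Second, a programmer who follows 5.4.2.2 as printed would count AE interruptions as missed capsules, while 5.4.2.1 does not. The same patient could then appear in different compliance bands in two tables of the same report, for reasons unrelated to adherence.

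A missing overall value also sends the patient to the C3 fallback. A negative answer there could reflect under-use, although the category is for over-use.

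**Working it through.** The plan states no rate of missing counts and no expected share of patients with calculable compliance, so there is no figure to reproduce.

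**Number of expected counts.** In the Protocol Flowchart, the row "Compliance / drug accountability" is marked at Visits 3, 5, 6, 7, 8, each Visit X and EOT. Visits 3 to 8 give 5 counts by Week 48. Visits 9 to 12 add 4, giving 9 by Week 96. Five further 12-weekly visits (Weeks 108 to 156) give 14 by about 36 months, the estimated trial length in Protocol 3.1. A separate EOT visit would add one.

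**Share losing the whole-trial value.** With k expected counts and missing probability p per visit, assumed independent between visits, the share lost is 1 - (1 - p)^k.

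| p (assumed) | k = 9 | k = 14 |
|---|---|---|
| 1% | 1 - 0.914 = 8.6% | 1 - 0.869 = 13.1% |
| 2% | 1 - 0.834 = 16.6% | 1 - 0.754 = 24.6% |
| 5% | 1 - 0.630 = 37.0% | 1 - 0.488 = 51.2% |
| 10% | 1 - 0.387 = 61.3% | 1 - 0.229 = 77.1% |

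Fewer than half of patients keep a value only if p exceeds 1 - 0.5^(1/k), which is 7.4% for k = 9 and 4.8% for k = 14.

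**Tilt toward short stays.** At p = 5%, a patient with 3 counts keeps the value with probability 0.95^3 = 0.857, against 0.630 with 9 counts, a ratio of 1.36. In a population made up of these two types only, the 3-count patients would form most of the calculable group only if they were already more than 0.630 / (0.857 + 0.630) = 42% of all patients.

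**Literal 48/96-week compliance.** Take a patient who swallows every capsule except during an AE interruption of i weeks, in a period of D weeks. Ignoring the one-day and half-day terms, the 5.4.2.2 formula gives (D - i) / D. With the 5.4.2.1 subtraction, the result is (D - i) / (D - i) = 100% in every case. The interruption lengths are the two maxima in Protocol Table 4.2.1: 1: 4 weeks for drug-related AEs, and 12 weeks for AEs or other events not considered drug related.

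| Interruption | D = 48 weeks | D = 96 weeks |
|---|---|---|
| 4 weeks | 44/48 = 91.7% | 92/96 = 95.8% |
| 12 weeks | 36/48 = 75.0% | 84/96 = 87.5% |

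Only the 12-week interruption over 48 weeks leaves the 80-120% band; it falls into the band from 50 to below 80%. For a patient who completes the window, the threshold is 0.2 x 48 = 9.6 weeks of interruption over 48 weeks, or 0.2 x 96 = 19.2 weeks over 96 weeks. Repeated interruptions, which Protocol 4.2.1 allows, can add up to that. A patient who stops early is more sensitive: 4 weeks interrupted out of 12 gives 8/12 = 66.7%.

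**The case against.** **The AE rule may carry over.** SAP 5.4.2.2 supplies only the expected-capsule period; the ratio and the categories must come from 5.4.2.1. The displayed whole-trial formula has no subtraction term either. The AE rule there is a general sentence, and SAP 7.3 promises a similar summary for 48 and 96 weeks. This is a fair reading. A reader might infer that the two sections flatly contradict each other, but the text does not establish that. It supports a likely inconsistency that should be settled in writing.

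**The losses may be small.** A reader might infer that whole-trial compliance will describe a selected minority, or mainly short-stay patients. Neither follows. No missing rate is given, and at 1% to 2% per visit 83% to 91% of patients keep their value at 9 counts. Missed counts clustered in the same patients would remove fewer patients than the independence formula shows. All patients are asked to stay 96 weeks. Remote visits are for exceptional circumstances, and deferred returns may be counted later. What stands is that the loss rises with follow-up and that the rule has no fallback for the compliance summary.

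**The gap will be visible.** SAP Section 7 already gives N, percentages based on the whole subject set, and a missing category where values are missing. That shows how many patients are lost, but not how much exposure time the remaining values cover.

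**Interruptions that the protocol itself calls for.** For liver-test gaps, Protocol 6.1 says "If the interval is more than 16 weeks, trial treatment should be interrupted". One might argue that such interruptions should also leave the denominator. But SAP 5.4.2.1 states its choice openly, and removing more off-drug time would move compliance further from actual intake. Off-treatment duration, dose intensity and the reasons for interruption are reported in any case (SAP 5.4.3.1 and 7.7). That is a matter of preference and is not part of this point.

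**Conclusion.** The point holds in limited form. The whole-trial rule is explicit and can remove an unknown share of patients, rising with the number of visits: 9% to 61% at 9 counts and 13% to 77% at 14. These ranges rest entirely on the assumed 1% to 10% missing per visit and on independence between visits.

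The 48/96-week formula, read literally, moves a fully adherent patient with a 12-week AE interruption from 100% to 75.0% over 48 weeks and to 87.5% over 96 weeks. A single 4-week interruption causes no change of band in a patient who completes the window. Whether the literal reading is intended is not clear from the text.

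The consequences are small. Compliance is descriptive, there is no per-protocol set, C3 excludes nobody, and the primary endpoint is AE incidence on the treated set. This is a worthwhile improvement to the SAP that leaves the trial's main conclusion untouched.

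**What to change.** **SAP 5.4.2.1.** Replace the all-or-nothing rule. Compute compliance over dispensing intervals with a reconciled count, as capsules taken divided by capsules expected in those same intervals. Where one visit's count is missed, bridge it with the next return, so that the two intervals are reconciled together. Report the share of exposure time covered, alongside the N and missing category already planned in Section 7.

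**SAP 5.4.2.2.** State that AE interruptions are subtracted as in 5.4.2.1 and that the same missing-count rule applies.

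**Cost.** A few sentences of SAP text and modest programming. Protocol 4.1.8 already requires records of use by each patient and of returns, so no new data are needed. The drawback is that some patients will contribute compliance for only part of their follow-up, which is why the coverage figure should accompany the table.

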5.4.2.2 Over 48 weeks and over 96 weeks

The number of capsules which should have been taken over 48 weeks and over 96 weeks respectively will be calculated as:

$$(Date \text{ of } last \text{ nintedanib } intake^{[1]} - Date \text{ of } first \text{ nintedanib } intake + 1) \times 2$$

^[1] Or Week 48/Week 96 compliance assessment, if earlier.

In case of last nintedanib intake happened until Week 48/Week 96 compliance assessment, half a day will be subtracted assuming that only one capsule was taken on day of last nintedanib intake.

5.4.3 Exposure

Only exposure in the extension trial will be considered.

5.4.3.1 Over the whole trial

Duration of exposure [days] over the whole trial will be calculated as

$$Date \text{ of } last \text{ nintedanib } intake - Date \text{ of } first \text{ nintedanib } intake + 0.5 \text{ days},$$

assuming that only one capsule was taken on day of last nintedanib intake. Treatment interruptions will not be subtracted from this duration of exposure.

Duration of exposure [weeks] will be calculated as

$$\frac{Duration \text{ of } exposure \text{ [days]}}{7}$$

Duration of exposure [months] will be calculated as

$$\frac{Duration \text{ of } exposure \text{ [days]}}{30.5}$$

Duration of exposure will be summarised as continuous variable [months] and in categories:

- <=3 months (91 days);
- >3 to <=6 months (182 days);
- >6 to <=12 months (365 days);
- >12 to <=18 months (547 days);
- >18 to <=24 months (730 days);
- >24 to <=36 months (1095 days);
- >36 months

Further categories might be defined if needed.

Duration of exposure on actual dose (100 or 150 mg bid) [months] will be calculated as

$$\frac{\text{Sum of each continuous duration of exposure to 100/150 mg bid [days]}}{30.5}$$

This duration of exposure will be adjusted for treatment interruptions, dose reductions and dose increases and will be summarised as continuous variable and in categories:

- No 100/150 mg
- <=3 months (91 days);
- >3 to <=6 months (182 days);
- >6 to <=12 months (365 days);
- >12 to <=18 months (547 days);
- >18 to <=24 months (730 days);
- >24 to <=36 months (1095 days);
- >36 months

Off-treatment duration [weeks] will be calculated as

$$\frac{\text{Sum of each continuous duration of off - treatment periods [days]}}{7}$$

Total dose [g] will be calculated as

$$\text{Duration of exp. on 100 mg [days]} * 0.2 \text{ g} + \text{Duration of exp. on 150 mg [days]} * 0.3 \text{ g.}$$

Dose intensity [%] will be calculated as

$$\frac{\text{Total dose [g]}}{0.3 \text{ g} \times \text{Duration of exposure [days]}} \times 100\%$$

Dose intensity [%] will be summarised as continuous variable and in categories:

- <=30%; >30 to <=50%; >50 to <=90%; >90 to <100%; =100%.
- <=90%, >90%

5.4.3.1.1 Exposure-related time-to-event analyses

Exposure-related time-to-event analyses will be performed for the following items:

- Time to first dose reduction [days]
- Time to first treatment interruption [days]
- Time to premature treatment discontinuation [days]
- Time to first dose reduction or treatment interruption [days]

Time-to-event [days] for exposure-related analyses is derived based on first nintedanib intake in extension trial as

$$\textit{Date of event/censoring} - \textit{Date of first nintedanib intake} + 1 \text{ day}$$

For the above mentioned time-to-event analyses subjects with no such event occurred during the extension trial will be censored according to the mechanism for censoring as described in [Table 5.4.3.1.1: 1.](#)

These time-to-event analyses will also be summarised in categories:

- <=1 month (31 days)
- >1 to <=3 months (91 days)
- >3 to <=6 months (182 days)
- >6 to <=12 months (365 days)
- >12 to <=18 months (547 days)
- >18 to <=24 months (730 days)
- >24 to <=36 months (1095 days)
- >36 months
- Censored

Further categories might be defined if needed.

